Treatment continuation criteria	
  
 Variable	Re-treatment	
 
 Day 1	
   
 ECOG-PS	≤ 2	
 
 Hemoglobin*	$\geq 8.0 \text{ g/dl}$	
 
 ANC	$\geq 1.5 \times 10^9/\text{l}$	
 
 Platelets	$\geq 75 \times 10^9/\text{l}$	
 
 AST/ALT	$\leq 3.0 \times \text{ULN}$	
 
 Total bilirubin or direct bilirubin	$\leq 1.5 \times \text{ULN}$ or $\times \text{ULN}$	
 
 Albumin	$\geq 2.7 \text{ g/dl}$	
 
 Serum creatinine	$\leq 2.0 \times \text{ULN}$	
 
 CPK	Grade ≤ 1	
 
 Other non-hematological drug-related AEs (except isolated increased GGT and/or AP[‡], grade 3 asthenia lasting < 1 week, non-optimally treated nausea and/or vomiting)	Grade ≤ 2	
  
 
* Patients may receive packed red blood cells (PRBC) transfusion and/or erythropoietin (EPO) treatment, if clinically indicated, to increase/maintain adequate hemoglobin levels.
 
[‡] Any grade accepted for non-drug-related increase of GGT and/or AP.
 
AE, adverse event; ANC, absolute neutrophil count; AP, alkaline phosphatase; AST/ALT, aspartate aminotransferase/alanine aminotransferase; CPK, creatinine phosphokinase; ECOG, Eastern Cooperative Oncology Group; GGT, gamma-glutamyltransferase; PS, performance status; ULN, upper limit of normal.
 
If a patient does not meet the requirements for re-treatment on Day 1 of any following cycle, regardless of the reason, reassessments will be performed every 48-72 hours. Treatment will be then withheld, up to a maximum of three weeks beyond its due date, until appropriate recovery.
 
Patients not meeting re-treatment criteria after a maximum three-week delay must be withdrawn from the trial, except in case of objective clinical benefit (upon Sponsors' agreement).
 
For any delay lasting more than one week due to treatment-related toxicity (unless exclusively due to neutropenia), a dose reduction must be implemented upon recovery following the rules explained in the next section. Conversely, if the delay was exclusively due to neutropenia related to PM01183, treatment may continue without dose reduction but with appropriate secondary prophylaxis with granulocyte colony-stimulating factor (G-CSF).
	Variable	Re-treatment	Day 1	ECOG-PS	≤ 2	Hemoglobin*	$\geq 8.0 \text{ g/dl}$	ANC	$\geq 1.5 \times 10^9/\text{l}$	Platelets	$\geq 75 \times 10^9/\text{l}$	AST/ALT	$\leq 3.0 \times \text{ULN}$	Total bilirubin or direct bilirubin	$\leq 1.5 \times \text{ULN}$ or $\times \text{ULN}$	Albumin	$\geq 2.7 \text{ g/dl}$	Serum creatinine	$\leq 2.0 \times \text{ULN}$	CPK	Grade ≤ 1	Other non-hematological drug-related AEs (except isolated increased GGT and/or AP [‡] , grade 3 asthenia lasting < 1 week, non-optimally treated nausea and/or vomiting)	Grade ≤ 2

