TREATMENT DISCONTINUATION	
Patients will receive study medication as long as it is considered to be in their best interest. Specifically, treatment will continue until:
 
 • Disease progression. • Unacceptable toxicity (except in case of clear clinical benefit, with the Sponsors' approval), after appropriate dose reduction. • Intercurrent illness of sufficient magnitude to preclude safe continuation of the study. • Patient refusal and/or noncompliance with study requirements. • Investigator's decision. • Protocol deviation with an effect on the management of the patient's risk/benefit ratio. • Treatment delay > 3 weeks from the treatment due date (except in case of clear clinical benefit, upon Sponsors' approval). • Requirement of > 2 dose reductions.
REPLACEMENT OF PATIENTS	
Patients will be replaced if they are not evaluable for the primary endpoint of the study (ORR as per RECIST v1.1), specifically (any of the following):
 
 • They are not eligible. • They have not been treated or have not completed at least one PM01183 infusion. • They are not evaluable for ORR as per RECIST v1.1 and they are not categorized as "treatment failures". Treatment failures will not be replaced and are defined as patients who: 
 ◦ Discontinue treatment due to any treatment-related toxicity before an appropriate tumor assessment has been performed, or ◦ Withdraw PM01183 after more than two weeks on treatment without any formal evaluation 
All replaced patients who received treatment will be included in the general safety analysis, if appropriate.

DURATION OF STUDY (as a whole)	
The total duration of the study will be approximately 72 months.
 
Planned start date (first patient on study): second quarter 2012 (2Q12).
 
Planned enrollment period: 60 months.
 
Planned study completion date (clinical cut-off): nine months after the last patient-last treatment visit in the study, or 12 months after the last evaluable patient is enrolled (whichever occurs first).

SCHEDULE OF ASSESSMENTS AND PROCEDURES

STUDY PERIODS ⁽¹⁾ PROCEDURES	Screening (days)	Treatment						Follow-up ⁽²⁾
		Cycle 1			Cycle 2		Further Cycles	
		D1	D8	D15	D1	D10	D1	
Written informed consent	Before any study procedure	-	-	-	-	-	-	-
Written informed consent - PGx substudy (optional for cohorts A and B)	Before any study procedure	-	-	-	-	-	-	-

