Patients will be evaluated using clinical and laboratory assessments before each treatment cycle (Sections [6.3](#) and [6.6](#)). Appropriate radiological and/or clinical tumor assessments will be done every six weeks until evidence of PD (Section [7.1](#)). Patients no longer receiving study treatment will be followed up for survival (Section [6.8](#)).

Any treatment-related AE will be followed until recovery to grade ≤ 1 or stabilization of symptoms, whenever possible (Section [7.2](#)). Reasons for dose reduction, treatment delays and/or treatment discontinuation will be documented as appropriate.

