5.2.2. Criteria for Treatment Continuation

Before the administration of each dose (re-treatment) on Day 1 of each cycle, patients must fulfill all of the criteria defined in [Table 2](#).

Table 2. Criteria for continuation of treatment.

Variable	Re-treatment
	Day 1
ECOG-PS	≤ 2
Hemoglobin*	≥ 8 g/dl
ANC	≥ 1.5 x 10 ⁹ /l
Platelets	≥ 75 x 10 ⁹ /l
AST/ALT	≤ 3.0 x ULN
Total bilirubin or direct bilirubin	≤ 1.5 x ULN or x ULN
Albumin	≥ 2.7 g/dl
Serum creatinine	≤ 2.0 x ULN
CPK	Grade ≤ 1
Other non-hematological drug-related AEs (except isolated increased GGT and/or AP [‡] , grade 3 asthenia lasting < 1 week, non-optimally treated nausea and/or vomiting)	Grade ≤ 2

* Patients may receive packed red blood cells (PRBC) transfusion and/or erythropoietin (EPO) treatment, if clinically indicated, to increase/maintain adequate hemoglobin levels.

[‡] Any grade accepted for non-drug-related increase of GGT and/or AP.

AE(s), adverse event(s); ANC, absolute neutrophil count; AP, alkaline phosphatase; AST/ALT, aspartate aminotransferase/alanine aminotransferase; CrCl, creatinine clearance; CPK, creatinine phosphokinase; ECOG, Eastern Cooperative Oncology Group; GGT, gamma-glutamyltransferase; PS, performance status; ULN, upper limit of normal.

If a patient does not meet the requirements for re-treatment on Day 1 of any following cycle, regardless of the reason, re-assessments will be performed every 48-72 hours. Treatment will be then withheld, up to a maximum of three weeks beyond its due date, until appropriate recovery.

Patients not meeting re-treatment criteria after a maximum three-week delay the patient must be withdrawn from the trial, except in case of objective clinical benefit (upon Sponsors' agreement).

For any delay lasting more than one week due to treatment-related toxicity (unless exclusively due to neutropenia), a dose reduction must be implemented upon recovery following the rules explained in the next section. Conversely, if the delay was exclusively due to neutropenia related to PM01183, treatment may continue without dose reduction but with appropriate secondary prophylaxis with granulocyte colony-stimulating factor (G-CSF).

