6.2. DURATION OF STUDY (PER PATIENT)

Patients will be individually evaluated at scheduled visits in up to three study periods:

- **Screening:** from signature of the ICF to first infusion of PM01183.
- **Treatment:** from first infusion of PM01183 to **end of treatment (EOT)**. **EOT** is defined as 30 days after the date of PM01183 last administration, unless the patient starts a new antitumor therapy or dies within those 30 days, in which case the date of administration of this new antitumor therapy or the date of death will be considered as EOT.
- **Follow-up:** after EOT, patients will be followed for any ongoing treatment-related AEs every four weeks until recovery to grade ≤ 1 , or until symptoms stabilization, whenever possible.

Patients will be followed for at least one year after their first infusion. Those who discontinued treatment without PD will be assessed every two months during the first six months after last tumor assessment and every three months thereafter, until

PD, start of other antitumor therapy, death, or study completion, whichever occurs first.

After documented PD or start of a new antitumor therapy, patients will be followed every six months until death or study completion, whichever occurs first. For the purpose of collecting information on the patient's survival exclusively, a documented telephone call would be acceptable.

Patients will be considered to be **on-study** from the signature of the clinical ICF to the end of the follow-up period (or screening failure).

Patients will be considered to be **on-treatment** from the date of first infusion of PM01183 until EOT.

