6.2.1.3. Off-study

Off-study occurs when an enrolled patient ceases to participate in the study, regardless of the reason. Patients have the right to withdraw consent at any time; if this is the case, no further follow-up should be performed.

The date and reason for study discontinuation will be clearly documented on the patient's CRF. If a patient is lost to follow-up an attempt will be made to collect the information on the patient's survival and date of death (when applicable).

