6.8. FOLLOW-UP AFTER END-OF-TREATMENT VISIT

The date and reason of the end of study will be recorded on the patient's CRF.

After the end of treatment, all AEs and SAEs suspected to be related to PM01183 must be followed-up until recovery to grade ≤ 1 or symptoms stabilization whenever possible (for safety reporting see Section [11.2](#)). Pregnancy and suspected pregnancy occurring within six weeks from the patient's last PM01183 administration are considered immediately reportable events.

Additionally, radiological and/or clinical tumor assessments will be done during the follow-up only to those patients who discontinue treatment without documented disease progression. Patients will be followed every two months during the first six months after last tumor assessment and every three months thereafter until PD, start of other antitumor therapy, death, or study completion (clinical cut-off), whichever occurs first.

After documented progression or start of a new antitumor therapy, patients will be followed every six months, until death or study completion (clinical cut-off), whichever occurs first. For this purpose of collecting information on the patient's survival exclusively, a documented telephone call would be acceptable and no visits to the hospital will be required.

Patients who withdraw consent will not be followed with any study procedures.

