#### Secondary endpoint

The following time-related parameters would be analyzed according to available follow-up data:

**Duration of response (DR)** is defined as time from first observation of response to the date of disease progression, recurrence or death. Other causes will be censored. Although the responses have to be confirmed according to RECIST v1.1 criteria, the first documentation, not the confirmation, will be taken into account to calculate DR. Patients who progress or die will be considered to have had an event, except if this event occurs after the start of subsequent antitumor therapy, in which case the patient will be censored at the time of last disease assessment prior to or on the first day of the first subsequent antitumor therapy.

**Clinical benefit rate** is calculated as the number of patients who have had CR or PR or SD  $\geq 3$  months as overall best response according to the RECIST v1.1 criteria, divided by the number of patients in the “All Evaluable Patients” analysis set.

**Progression-free survival (PFS)** is defined as the time from start of treatment to the date of documented progressive disease (PD) by RECIST v1.1 criteria or death (regardless of the cause of death), whichever comes first. Patients who progress or die will be considered to have had an event, except if this event occurs after the start of subsequent antitumor therapy, in which case the patient will be censored at the time of last disease assessment prior to or on the first day of the first subsequent antitumor therapy. If the patient is lost for the assessment of progression during the follow-up period, or has more than one missing follow-up between the date of last tumor assessment and the date of progression, death or further antitumor therapy, the PFS will be censored at the date of last valid disease assessment before the missing evaluations.

**Overall survival (OS)** is defined as the time from the date of start of treatment to the date of death or last contact. **1 year overall survival (1y-OS)** is defined as the Kaplan-Meier estimate of the probability of patients alive after 12 months from the date of start of treatment.

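### A delay of more than three weeks is withdrawal from the trial in Section 5.2.2 but only end of treatment in Section 6.2.1.2; read literally, 5.2.2 could cost PFS and one-year OS follow-up

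*Protocol*

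**What the plan says.** Four operative passages of the protocol deal with a patient who has not recovered enough to be re-treated within three weeks of the due date.

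- Section 5.2.2 (Criteria for Treatment Continuation): "after a maximum three-week delay the patient must be withdrawn from the trial, except in case of objective clinical benefit", with the Sponsors' agreement needed for the exception.
- Synopsis, Treatment continuation criteria: "Patients not meeting re-treatment criteria after a maximum three-week delay must be withdrawn from the trial", with the same exception.
- Synopsis, Treatment discontinuation, and Section 6.2.1.2 (Reasons for End of Treatment) carry the same item in a list of reasons for stopping the drug: "Treatment delay > 3 weeks from the treatment due date (except in case of clear clinical benefit, upon Sponsors' approval").

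Section 6.2.1.1 defines treatment discontinuation as no longer receiving study medication. Section 6.2.1.3 defines a different state: "Off-study occurs when an enrolled patient ceases to participate in the study, regardless of the reason".

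For patients who stop the drug, the protocol continues observation:

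- Section 2: "Patients no longer receiving study treatment will be followed up for survival".
- Section 6.2: "Patients will be followed for at least one year after their first infusion".
- Section 6.8: tumor assessments continue, "only to those patients who discontinue treatment without documented disease progression", every two and later every three months, until progression, new therapy, death or cut-off.

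**The concern.** The same event has two stated outcomes, and each pair of statements conflicts within its own part of the protocol: synopsis against synopsis, and Section 5.2.2 against Section 6.2.1.2. Because the protocol separates stopping treatment from leaving the study, the choice of words has consequences. Withdrawal from the trial, read plainly, matches the off-study definition.

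The sentence is mandatory and sits where a site will look when a patient fails the criteria in Table 2. If it is applied as written, tumor assessments and survival contact could stop. PFS and one-year OS are named secondary endpoints estimated by Kaplan-Meier, which assumes non-informative censoring. The criteria that trigger the rule include ECOG performance status, albumin, bilirubin and unresolved drug-related adverse events. Failing them may be related to prognosis, so censoring these patients could bias both estimates.

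**Working it through.** The plan gives no figure to reproduce here. The check compares the texts and then does one piece of timing arithmetic.

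**1. Is it the same event?** Section 5.2.2 withholds treatment for at most three weeks past the due date and acts if the criteria are still not met. Section 6.2.1.2 acts on a delay of more than three weeks from the due date. Both carry an exception for clinical benefit that needs the Sponsors' consent. The trigger is the same.

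**2. Are the outcomes different?**

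| Place | Stated outcome |
|---|---|
| Section 5.2.2 | Withdrawal from the trial |
| Synopsis, Treatment continuation criteria | Withdrawal from the trial |
| Section 6.2.1.2 | End of treatment |
| Synopsis, Treatment discontinuation | End of treatment |

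Sections 6.2.1.1 and 6.2.1.3 keep the two states apart, so the outcomes do differ.

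**3. Which outcome is intended?** Sections 2, 6.2 and 6.8 all require follow-up after treatment stops. The only ground on which the protocol says follow-up is to cease is withdrawal of consent (Sections 6.2.1.3 and 6.8). In the SAP, Table 10.2.5 (study discontinuation) has no category for prolonged delay, so such a patient would have to go under Other. The intended outcome is to stop the drug and keep observing.

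**4. What happens in the analysis if Section 5.2.2 is followed literally?** Under SAP Section 6.1, if the patient is lost to progression assessment, "the PFS will be censored at the date of last valid disease assessment before the missing evaluations". OS runs to death or last contact, so she is censored at her last contact.

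**5. How much could one patient lose?**

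- Cycle 2 due: week 3 (three-week cycle, Section 5.2.1).
- Maximum delay: 3 weeks (Section 5.2.2).
- Earliest date the rule can apply: 3 + 3 = 6 weeks from first infusion.
- Remaining time to the one-year OS landmark: 52 − 6 = 46 weeks.
- Post-baseline tumor data by then: at most the week-6 scan, since assessments are every six weeks (Section 7.1).

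**6. How many patients?** The documents give no expected frequency of delays beyond three weeks, so the total loss cannot be calculated.

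**The case against.** The best defense is that this is loose wording which the protocol itself resolves. The sentence stands in the treatment chapter, directly after the instruction to withhold the drug, and its exception only makes sense as permission to keep dosing. The protocol is informal with these terms elsewhere. Section 11.1.1 speaks of discontinuation from the trial where the parallel criterion in Section 11.2.1 speaks of study treatment. Section 11.2.3 requires withdrawal from the trial for a continued pregnancy and yet has the investigator follow the pregnancy to its outcome. Section 6.2.1.1 asks for every effort to complete assessments after discontinuation, Section 6.7 requires the end-of-treatment work-up whatever the reason for stopping, and Section 6.2.1.3 asks for survival status even in patients lost to follow-up. Harm would need a site to read one sentence in isolation and to go uncorrected at monitoring.

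Much of this stands. Most sites would probably read the rule as intended, the endpoints concerned are secondary and carry no confirmatory test, and the 46-week figure is a worst case, not an expected loss. But these arguments show which reading is right; they do not remove the contrary instruction. Where the protocol means stopping the drug in its treatment-failure definition (Sections 6.10 and 7.1), it names the drug. The survival-status provision in Section 6.2.1.3 is written for patients lost to follow-up, and does not clearly cover one whom the protocol told the site to withdraw.

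**Conclusion.** The inconsistency is real and the sentence is wrong as written in both places. It is minor. The possible loss is PFS and one-year OS follow-up in patients who fail re-treatment criteria, with censoring that could be informative. For one patient the upper bound is 46 of 52 weeks. That assumes failure at Cycle 2, no recovery, literal application of Section 5.2.2 and no later retrieval of survival status. The number of such patients is unknown.

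There is no material effect on ORR, alpha, power or sample size; patients with objective benefit can be kept on treatment under the exception. Follow-up of related adverse events is required separately in Sections 11.2.1 and 11.2.2 and is not in question.

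**What to change.** In Section 5.2.2 and in the synopsis continuation criteria, replace the instruction to withdraw the patient from the trial with: *must discontinue study treatment (Section 6.2.1.2) and be followed as per Section 6.8*. Keep the clinical-benefit exception.

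The cost is one sentence in two places. It adds no visits or procedures, because Sections 2, 6.2 and 6.8 already require this follow-up, and the SAP needs no change.

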5.2.3. Dose Reduction

Study treatment may continue with an appropriate dose reduction ([Table 3](#)) if patient benefit is perceived by the Investigator (upon Sponsors' agreement), even after the patient experienced any of the following:

- Grade ≥ 3 treatment-related non-hematological toxicity. Exceptions are: grade 3 nausea and/or vomiting not optimally treated, grade 3 asthenia lasting < 1 week, grade 3 diarrhea lasting ≤ 2 days or not optimally treated, grade 3-4 hypersensitivity and/or extravasation reactions, grade 3 transient ALT/AST elevations which are rapidly reversible and not leading to subsequent delays, and/or not clinically relevant biochemical abnormalities [i.e., in gamma-glutamyltransferase (GGT), lactate dehydrogenase (LDH) and/or alkaline phosphatase (AP) levels], none of which require dose reduction to be implemented.
- Grade 4 thrombocytopenia or grade 3 thrombocytopenia concomitantly with grade ≥ 3 bleeding.
- Frequent or prolonged (>1 week) dose delays due to treatment-related toxicity.

Patients experiencing grade 4 neutropenia or febrile neutropenia during the preceding cycle, or treatment delays exclusively due to neutropenia that lasted >1 week, may continue treatment without any dose reduction but must receive secondary prophylaxis with G-CSF instead. The G-CSF secondary prophylaxis will be administrated subcutaneously at 300 μ g/day for five consecutive days starting on Day +3 of the corresponding cycle. If despite appropriate G-CSF prophylaxis, grade 4 neutropenia or febrile neutropenia re-occurs, then dose reduction should be implemented.

Table 3. Guidelines for dose reduction.

Dose reduction level*	PM01183 dose (mg, FD) Patients included under protocol versions 1.0, 2.0	PM01183 dose (mg/m ²) Patients included from protocol version 3.0 onward**
1	7.0	3.5
-1	6.0	2.6
-2	5.0	2.0

* Except for grade ≥ 3 nausea and/or vomiting not optimally treated, grade 3 asthenia lasting < 1 week, grade 3 diarrhea lasting ≤ 2 days or not optimally treated, grade 3-4 hypersensitivity and/or extravasation reactions, grade 3 transient ALT/AST elevations which are rapidly reversible and not leading to subsequent delays, and/or isolated not

clinically relevant biochemical abnormalities (i.e., GGT, LDH and/or AP), none of which require dose reduction to be implemented.

**Dose will be capped at BSA of 2.0 m² (starting dose will not exceed 7 mg). BSA will be calculated according to standard practice at each center.

ALT/AST, aspartate aminotransferase/alanine aminotransferase; AP, alkaline phosphatase; FD, flat dose; GGT, gamma-glutamyltransferase; LDH, lactate dehydrogenase.

Up to two dose reductions are allowed per patient.

Once the dose has been reduced for an individual patient, it will not be re-escalated under any circumstances.

